10.2 Primary Efficacy Hypothesis

The primary efficacy hypothesis for this study is formulated in terms of clinical non-inferiority and is consistent with the Blackwelder approach (Blackwelder, 1982). Symbolically, the null and alternative hypotheses may be expressed as follows:

Ho: $\pi_{\text{Eclipse}^{\text{TM}}} - \pi_{\text{Univers II}^{\text{TM}}} \leq -\delta$ (investigational device inferior)

Ha: $\pi_{\text{Eclipse}^{\text{TM}}} - \pi_{\text{Univers II}^{\text{TM}}} > -\delta$ (investigational device not inferior)

The π represents the proportion (or probability) of devices expected to achieve Month 24 Composite Clinical Success. Thus, this study is designed to demonstrate that π for investigational device is no more than δ less than π among control devices. For $\delta = 0.10$, these hypotheses may be written as:

Ho: $\pi_{\text{Eclipse}^{\text{TM}}} - \pi_{\text{Univers II}^{\text{TM}}} \leq -0.10$

Ha: $\pi_{\text{Eclipse}^{\text{TM}}} - \pi_{\text{Univers II}^{\text{TM}}} > -0.10$

10.3 Secondary Outcomes

Descriptive analyses will be performed on the secondary efficacy endpoint. Continuous variables including function scores will be summarized for each device group pre-operatively and at each planned follow-up visit (Post-op, Month 3, Month 6, Month 12, and Month 24) using means, SDs, medians, minimum, and maximum values. Standardized effect sizes (mean difference divided standard deviation of differences) will be computed at each time point for each continuous measure in order to facilitate assessment of group differences across measures as well as time. Pooled t-tests and Wilcoxon rank sum tests will be provided as additional descriptive measures. Categorical secondary efficacy endpoints will be compared between groups

using counts and percentages. Descriptive chi-square tests will be provided for secondary categorical efficacy endpoints. There will be no imputation of missing values for secondary endpoints and no control for type I error in the set of secondary endpoints. Graphical displays of selected endpoints will be provided to provide visual assessments of group differences over time.

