3.2.3 Secondary Endpoints

The following will be evaluated as secondary endpoints:

- Adjusted Constant scores and radiographic success evaluated at each time point.
- The percentage of patients achieving an Adjusted Constant Score ≥ 70 at each time point.
- SF-36
- VAS

4 Study Population: Inclusion and Exclusion Criteria

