6.2 Preoperative Evaluation: Visit 1 (-21 to day 0)

Once the subject has signed the informed consent and prior to surgery, they will have the following data collected and procedures conducted: (Appendix 2-5 Case Report Forms)

- Demographics /History CRF
 - Kellgren-Lawrence Scale
 - Staging System of Cruess
 - American College of Rheumatology
 - SCORE/MORES questionnaire
- Concomitant Medication & Therapy CRF (pain management only)
- Subject Report Survey's:

Note: Subject surveys are to be completed prior to the Physical, The survey should be QC'd for completeness, discrepancies, signed or initialed and dated, during the visit.

- SF36
- VAS
- Constant Score:
 - Subject will be asked to fill out the subject section regarding activities of daily living (sleep, work, recreation / sport).
 - Clinician completes objective section by assessing range of motion and strength
- Physical Exam/Shoulder Exam includes sensory and motor testing

- Radiograph(s)
- Note:
 - Serum or urine Pregnancy test if applicable
 - Enrollment Checklist
 - Patient Education regarding Total Shoulder Prosthesis, post-operative procedures and the follow-up study schedule.
 - Inform subjects that they will return post-op within 3 months, 6 months, 12 Months and 24 Months for follow-up.
 - Deviations
 - Note: Screening procedures may be done on different days within the screening window.

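### Minor, free improvement: Section 10.3 names no baseline-adjusted comparison for the continuous secondary endpoints and does not say whether its tests use visit values or change

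*Combined protocol and SAP*

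**What the plan says.** Section 3.2.3 lists among the secondary endpoints "Adjusted Constant scores and radiographic success evaluated at each time point", together with SF-36 and VAS. Section 6.2 introduces the Visit 1 data with "Once the subject has signed the informed consent and prior to surgery, they will have the following data collected and procedures conducted", and the list that follows contains SF-36, VAS and the Constant Score. The same three measures are repeated at Months 3, 6, 12 and 24 (Sections 6.4 to 6.6 and the Schedule of Events).

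Section 10.3 sets the status of the analysis: "Descriptive analyses will be performed on the secondary efficacy endpoint". Continuous measures are to be "summarized for each device group pre-operatively and at each planned follow-up visit". It adds "Standardized effect sizes (mean difference divided standard deviation of differences) will be computed at each time point", and then "Pooled t-tests and Wilcoxon rank sum tests will be provided as additional descriptive measures". It closes with "There will be no imputation of missing values for secondary endpoints and no control for type I error in the set of secondary endpoints".

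Section 10.3 names no ANCOVA, mixed model, adjusted difference or confidence interval for these endpoints. The only covariate adjustment of a treatment comparison in Section 10 is in 10.5.1. That is a logistic regression for the binary composite (CCS), used only if a clinically important baseline imbalance appears.

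**The concern.** A pre-operative score usually predicts part of the later score. A two-sample test on visit values leaves that part in the error term, and it leaves any baseline difference between the arms in the estimate. A test on change uses the baseline but gives it a fixed weight of one, which can be less precise than ignoring it when the correlation is low. Section 10.3 does not say which of these is intended. The phrase about the standard deviation of differences could refer to change within patients or to the difference between groups.

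The stake is the quality of the reported group differences in function, pain and health status. Two features of this trial make adjustment a little more useful than usual.

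- **Control enrolment.** Section 3.1 allows control randomization to halt after 77 while Eclipse enrolment continues. At 2:1, 77 controls correspond to about 154 concurrent Eclipse patients, so reaching 196 would add about 42 who were not randomized alongside controls. Adjustment can address measured baseline differences in that part, though not unmeasured ones.
- **Missed visits.** Missing secondary values are not imputed, so a patient with no data at a visit drops out of that visit's comparison.

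**Working it through.** **1. Inputs and the plan's own figures.** Section 10.1, Table 1 gives a post-operative Adjusted Constant SD of 22.8. The inclusion-criteria section, Table 3, gives a pre-operative mean of 37.3 and SD of 15.6. Both SDs reproduce as size-weighted averages of the studies in Appendix 2-11 (Constant Score Calculations):

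- Post-operative: (705×23.5 + 42×13.4 + 17×17)/764 = 22.8
- Pre-operative: (518×16.5 + 42×6.3 + 17×11.7)/577 = 15.6

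The arm sizes in Section 10.4 also reproduce: (1.645 + 0.842)² × 0.88×0.12 × 1.5 / 0.10² = 97.9. This rounds up to 98 controls, with 196 Eclipse. The documents give no precision or power figure for any secondary endpoint, and no SD for VAS or SF-36.

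**2. Unadjusted precision, visit values.** SE = SD × √(1/n_c + 1/n_t).

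- 98 vs 196: 22.8 × √(1/98 + 1/196) = 2.82; 95% half-width 1.96 × 2.82 = 5.53 points
- 77 vs 196: 22.8 × √(1/77 + 1/196) = 3.07; half-width 6.01 points

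**3. With the baseline as a covariate.** Assuming the same SD and slope in both arms, the residual SD is 22.8 × √(1−ρ²). The correlation ρ is not in the documents, so a range is shown.

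| Assumed ρ | Half-width, 98/196 | Half-width, 77/196 | Interval narrower by |
|---|---|---|---|
| 0.2 | 5.42 | 5.89 | 2% |
| 0.3 | 5.27 | 5.73 | 5% |
| 0.5 | 4.79 | 5.21 | 13% |
| 0.7 | 3.95 | 4.29 | 29% |

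**4. Effect of the entry limit.** Inclusion criterion 4 requires a baseline score of 50 or less. Take a normal baseline (37.3, SD 15.6) truncated at 50. The cut is at (50 − 37.3)/15.6 = 0.814 SD, and the SD falls to about 11.8. With k = 11.83/15.6 = 0.758, the correlation among enrolled patients is ρk / √(1 − ρ² + ρ²k²).

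- ρ = 0.3 becomes 0.23: interval about 3% narrower, or 0.15 of 5.53 points
- ρ = 0.5 becomes 0.40: interval about 8% narrower, or 0.46 of 5.53 points

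**5. If the tests use change scores.** SD of change = √(15.6² + 22.8² − 2ρ×15.6×22.8). This exceeds 22.8 whenever ρ is below 15.6/(2×22.8) = 0.34, or below 11.8/(2×22.8) = 0.26 if the truncated baseline SD applies. With the untruncated SDs:

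- ρ = 0.3: change 23.45, visit value 22.8, adjusted 21.75
- ρ = 0.5: change 20.19, visit value 22.8, adjusted 19.75

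The adjusted analysis is the most precise of the three at both values, so the suggestion does not depend on which reading of 10.3 is right.

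**6. VAS and SF-36.** Without SDs only the factor √(1−ρ²) applies, and no gain in points can be stated. Neither measure has an entry limit of its own.

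**The case against.** The strongest reply is that the plan makes these tests peripheral. The comparison rests on summaries, effect sizes and graphs; the tests are additional, type I error control is disclaimed, and no success criterion uses them. That stands, and it is why the point is minor. It does not remove the point, because the reported differences would still be better estimated with the baseline included.

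Several stronger readings are tempting, and the documents do not support them.

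- **That the baseline data are thrown away.** They are summarised pre-operatively under 10.3. The baseline Constant Score enters the primary endpoint through the required 10-point gain, and 10.5.1 compares baseline shoulder assessment between arms.
- **That the tests certainly ignore baseline.** Visit values are the natural reading, but the text does not exclude change scores.
- **That the loss is large.** At ρ = 0.5 the gain equals 1/(1 − 0.25) − 1 = 33% more patients. That correlation is assumed, and after the entry limit the figure is nearer 1/(1 − 0.40²) − 1 = 19%. For an unrestricted 0.3 it falls from 10% to about 6%.
- **That missed visits are neglected.** The Schedule of Events notes allow the three instruments at an unscheduled visit when a time point was missed, and call for end-of-study procedures on early termination. No per-visit missing rate is given, so the benefit of a repeated-measures model cannot be sized.
- **That stopping controls at 77 creates an imbalance.** None can be shown from the documents. The SE rises from 2.82 to 3.07, about 9%, and Section 3.1 says the number of controls may end slightly higher.

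**Conclusion.** The point holds as a minor improvement. Section 10.3 specifies no baseline-adjusted group difference for the continuous secondary endpoints, although the pre-operative values are in hand, and it leaves the tested quantity undefined. For the Adjusted Constant Score the likely gain is small to modest: a few percent of interval width for correlations up to about 0.3, and about 8% to 13% at 0.5, depending on whether the entry limit is allowed for.

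These sizes rest on the literature SDs, an assumed correlation, a common slope and SD in the two arms, and a normal baseline for the truncation step. A reader might infer that the non-inferiority conclusion is at risk. It is not: the primary CCS test and its sample size do not use these comparisons.

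**What to change.** Amend Section 10.3 as follows.

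1. State whether the t-tests, Wilcoxon tests and effect sizes use visit values or change from baseline, and which standard deviation is the divisor.
2. For each continuous secondary endpoint, add a baseline-adjusted group difference with a 95% CI. ANCOVA at each visit with group and the pre-operative value is enough. A repeated-measures model with group, visit, group-by-visit and baseline is an alternative that also uses partial follow-up.
3. Keep the t-test and Wilcoxon results as supportive, and keep the descriptive label.

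The cost is SAP wording and routine programming, with no new data, visits or patients.

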10.4 Sample Size Analysis for Primary Non-Inferiority Test

Given the above criteria, the Sponsor expects a success rate of 88% for both the Eclipse and control group.

To determine the required sample size, it was assumed that the above primary hypotheses will be tested using 1-sided $\alpha=0.05$ at a statistical power of at least 80%. Under these assumptions, nQuery Advisor 7.0 module PTE0U-1 produces the following:

“When the sample sizes in the groups are 98 and 196, a two-group large-sample normal approximation test of proportions with a one-sided 0.05 significance level will have 80% power to reject the null hypothesis that the test and the standard are not equivalent (the difference in proportions, $p_T - p_S$, is -0.10 or farther from zero in the same direction) in favor of the alternative hypothesis that the proportions in the two groups are equivalent, assuming that the expected difference in proportions is 0.00 and the proportion in the standard group is 0.88.

Therefore, the total number of Per Protocol (Efficacy Evaluable) patients required under these assumptions are $N=294$. The number of protocol violations of inclusion / exclusion criteria (i.e., randomized in error) is expected to be small. The randomized sample size is adjusted up by 15% to account for both loss-to-follow-up and exclusions due to protocol violation to $N=347$.

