3.1 Study Design

Prospective, randomized, multi-center, clinical study. Up to twenty centers will randomize up to 350 subjects who are candidates for a Total Shoulder Arthroplasty, to 2 treatment groups in a 2:1 (Eclipse: Univers II) fashion. FDA has agreed that randomization of controls may be halted after N=77, with continuing enrollment of Eclipse until the originally planned Eclipse sample size target is reached. Given the timing needed for approval to stop control enrollment, the actually number of evaluable randomized controls may be slightly larger. This study will cease enrollment and be terminated if the Eclipse Shoulder Prosthesis receives 510 (k) clearance prior to all subjects completing the study.

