10.1 Definition of Month 24 Composite Clinical Success (CCS)

A literature search was conducted to estimate expected post-operative Constant scores and subjective success rate of TSA procedures. Fifteen (15) articles were found [1-15]. Four (4) articles were excluded due to data that appeared to be from the same data base and may contain the same subjects. The 11 included articles contained data on a total of 1095 subjects. All 11 of the articles contained post-operative Constant Scores, and 6 contained standard deviation associated with the post-operative Constant Score. Four (4) of the articles contained age/sex Adjusted Constant Scores and 3 out of those 4 contained standard deviation associated with the age/sex adjusted Constant Score. Four (4) of the 11 articles contained subjective satisfaction scores. The entire compilation can be seen in Appendix 2-12. Weighted averages based on sample size were calculated for Constant Scores, standard deviations, and percent satisfied using the compiled literature. The data is summarized in Table 1.

Table 1: Summarized weighted averages

Constant Score	66.2 ± 16.2
Adjusted Constant Score	87.6 ± 22.8
% Good/Satisfied or Better	93%
# of Subjects	1095

The data suggest that 93% of subjects were satisfied or better with the outcomes of TSA. Any pass/fail criterion for minimum acceptable Constant Score should produce an over-all success rate for non-investigation devices similar to those reported in literature (93%). To estimate the range of Constant Scores that would include 93% of the subjects, an 86% prediction interval was calculated. The results of the prediction interval can be seen in Table 2, and the calculation is illustrated in

Figure 1.

Table 2: Calculated prediction interval

	86% PI	Minimum Score
Constant Score	23.9	42.3
Adjusted Constant Score	33.7	53.9

Based on the literature available, a minimum Adjusted Constant score of 53.9 (or ≥ 54) should produce a pass rate of approximately 93%.

[figure not shown]

Figure 1: Adjusted constant score distribution plot

10.2 Determining the Adjusted Constant Score for Inclusion Criteria:

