Grade 4: Complete radiolucency (> 2 mm wide) around 2 or more pegs

Grade 5: Gross loosening

Success Criterion for Glenoid Radiolucency: Grade ≤ 3 glenoid Radiolucency

- **Rationale:** Previously, researchers have utilized a glenoid lucency of ≥ 4 (per criteria of Lazarus 2002) to determine those patients “at risk” for device malfunction due to glenoid lucency as 24 Months post-op. Haines et al. (2006) observed, in a prospective clinical trial of shoulder arthroplasties (n=124 shoulders, n=113 patients), 14% of patients at > 24 Months had a glenoid lucency score ≥ 4 (per criteria of Lazarus 2002). These patients, having what the authors describe as “at risk” implants, demonstrated a 78% survival rate at seven years, but only a 46% survival rate at ten years, compared to a survival rate of 84% at 10 years for the entire patient cohort. (Haines et al. 2006)

Glenoid Migration/Subsidence

Glenoid Migration/Subsidence will be graded as ‘Absent’ or ‘Present’

- **Absent:** Glenoid component displacement ≤ 3 mm relative to the baseline time point
- **Present:** Glenoid component displacement > 3 mm relative to the baseline time point

Glenoid Migration/Subsidence Endpoints will be assessed for change relative to month 3 image.

Success Criterion for Glenoid Migration: Absent Glenoid Migration/Subsidence**Device Condition**

Device Condition will be evaluated to assess the condition and integrity of the device. Device Condition will be graded as ‘Intact’, ‘Disassembly’ or ‘Fracture’ in accordance with the following definitions:

- **Intact:** No evidence of fractured or disassembled hardware. The hardware is intact.
- **Disassembly:** Presence of device component disassembly
- **Fracture:** Presence of fracture or breakage of one or more device components

Success Criterion for Device Condition: Intact device condition**Periprosthetic Fracture**

Periprosthetic fracture will be graded as ‘Absent’, ‘Present – Humeral’ in accordance with the following definitions:

- **Absent:** No evidence of periprosthetic fracture(s) about the humeral or glenoid components

- **Present – Humeral:** Presence of periprosthetic fracture(s) about the humeral component that is not present on the relative baseline time point

Success Criterion for Periprosthetic Fracture: Absence of device-related Periprosthetic fracture

4. No reoperation, removal, or modification of any study component up to the subject's completion of the study

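### The 88% expected composite success rate behind the 80% power has no derivation and conflicts with the protocol's own component figures, which would imply 79% to 86% and power of about 63% to 75%

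*Combined protocol and SAP*

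**What the plan says.** Section 10.4 gives the planning rate in one sentence: "Given the above criteria, the Sponsor expects a success rate of 88% for both the Eclipse and control group". It then sizes the trial for "1-sided $\alpha=0.05$ at a statistical power of at least 80" percent. The software statement begins "When the sample sizes in the groups are 98 and 196" and assumes a true difference of zero. The margin is in the primary efficacy hypothesis: "For $\delta = 0.10$, these hypotheses may be written as" a difference of -0.10. Section 3.1 randomizes "to 2 treatment groups in a 2:1 (Eclipse: Univers II) fashion" and lets control randomization stop after 77 controls while Eclipse enrolment continues to its original target.

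The criteria that the 88% refers to are in the CCS definition. Section 3.2.2 requires a patient to meet every component. Section 10.1 derives the Adjusted Constant Score cut-off of 54 from literature averages and says that it "should produce a pass rate of approximately 93" percent. For the glenoid the rule is "Success Criterion for Glenoid Radiolucency: Grade ≤ 3 glenoid Radiolucency", so grade 4 or 5 is a CCS failure. The rationale under that rule cites a prospective cohort of 124 shoulders in 113 patients, in which "14% of patients at > 24 Months had a glenoid lucency score ≥ 4".

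**The concern.** An 88% success rate allows 12% failures in total, from all components together. The only glenoid lucency rate in the protocol is 14%, which exceeds that allowance before any patient fails on function. Function itself is set to fail about 7%. After that, 88% leaves about 5 points for every radiographic, reoperation and serious device-related failure. Both arms use Univers glenoid components (Sections 2.4, 7.2 and 7.3), so a glenoid failure rate bears on both.

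Power is at stake. For rates above one half, a lower common success rate means a larger variance of the difference. The same 98 and 196 patients then give a truly non-inferior device a smaller chance of passing. Type I error and bias are not affected.

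**Working it through.** **Inputs**
- Margin 0.10; one-sided alpha 0.05 (z = 1.645); equal true rates p in both arms; 98 control and 196 Eclipse evaluable (Sections 10.2 and 10.4).
- Functional pass rate 0.93 (Section 10.1), so functional failure is 0.07.
- Glenoid grade 4 or worse: 0.14, beyond 24 months, in one external cohort (Section 10.1, glenoid rationale). Applying it at Month 24 is an assumption.
- Control halt at 77 (Section 3.1), taken here as 77 evaluable controls with 196 Eclipse. If 77 counts randomized patients, power is lower than shown.

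**Step 1: reproduce the plan.** Power = Φ(0.10/SE − 1.645), with SE = √[p(1−p)(1/98 + 1/196)]. At p = 0.88, SE = √(0.1056 × 0.015306) = 0.0402, and Φ(2.487 − 1.645) = Φ(0.842) = 80.0%. The matching sample-size formula returns 98 controls and 196 Eclipse. The stated figure is therefore right for p = 0.88.

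**Step 2: CCS implied by the two component figures, with no other component failing**
- Failures never overlap: 1 − 0.07 − 0.14 = 0.79.
- Independent failures: 0.93 × 0.86 = 0.80.
- Full overlap: 1 − 0.14 = 0.86.

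**Step 3: power at those rates**

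| CCS in both arms | Power, 98/196 | Power, 77/196 | Evaluable patients for 80% power at 2:1 |
|---|---|---|---|
| 88% | 80.0% | 74.0% | 98 + 196 = 294 |
| 86% | 75.3% | 69.1% | 112 + 224 = 336 |
| 80% | 64.6% | 58.4% | 149 + 298 = 447 |
| 79% | 63.3% | 57.2% | 154 + 308 = 462 |

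An exact binomial calculation for the same test at 98/196 gives 81.9%, 76.9%, 65.1% and 63.8%. These are all within 2 points of the normal approximation, and the pattern is the same.

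**Step 4: what 88% requires.** Suppose function passes 93% and other failures are independent of it. The remaining components together must then pass 0.88/0.93 = 94.6%, so at most 5.4% may fail on all of them combined. With full overlap, a glenoid failure rate of up to 12% fits 88%. With no overlap the limit is 5%.

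**Step 5: how firm the 14% is.** The protocol gives no count. Assuming 16/113 or 17/124, the exact 95% interval is about 8% to 22%. If the true rate were half the cited one (7%), CCS would be 86% with no overlap, 86.5% under independence (power 76.4% at 98/196) and 93% with full overlap.

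**The case against.** A reader might infer that the 14% caps CCS at 86%, that 88% is out of reach, and that the design simply lacks its stated power. The documents do not support that reading, for four reasons.

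- **Timing.** The cited figure is for patients beyond 24 months, with no stated upper limit, in a cohort whose 7- and 10-year survival is reported alongside it. CCS is read at 720 ± 60 days. Later films could show more lucency.
- **Purpose.** The cohort is cited to justify grade 4 as the cut-off, not as the rate expected in this trial. Its implants, indications and length of follow-up are not given, and the report is not listed in Section 11. The trial also excludes Walch B2 and C glenoids, irreparable cuffs and osteoporosis, which could lower the rate.
- **Sampling error.** The interval of about 8% to 22% includes rates below 12%, which fit 88% if functional and lucency failures largely coincide.
- **Conditionality.** The power sentence in Section 10.4 states its 88% assumption, and on that assumption it is correct. This is a dispute about an input, not a calculation error.

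All four stand, and they rule out the words cap and unattainable. They do not remove the conflict. Section 10.4 ties 88% to the listed criteria, and the only two component rates given with those criteria do not produce it. The escape through sampling error needs substantial overlap: under independence 88% tolerates 5.4% for all other failures combined, which is below the lower end of the interval. The other components are unlikely to be zero either. Section 5.1 reports 7% aseptic loosening of the humeral head, although without a time frame and not on the CCS definition.

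**Conclusion.** The point holds as an internal conflict in a planning figure. The 88% is underived and does not agree with the 93% functional pass rate and the 14% lucency rate that the protocol sets beside it. If the cited rate applied at Month 24, CCS would be 79% to 86%. Power at 98/196 would be about 63% to 75%, a loss of roughly 5 to 17 points from the stated 80%. Any further component failures would lower it again, as would stopping controls at 77.

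This rests on transferring a single external rate with open-ended follow-up to Month 24, and on equal true rates in the two arms. It does not show that 88% is wrong or that 86% is a ceiling. It shows that the protocol gives no reason to rely on 88%, and that its own figures point lower.

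**What to change.** In Section 10.4:

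1. Build the expected CCS from component rates: function, glenoid lucency, and an allowance for the remaining radiographic, reoperation and serious device-related failures. State the overlap assumed.
2. State the glenoid rate used for Month 24. If it differs from 14%, say why, for example follow-up time, implant or patient selection.
3. Replace the single power statement with power across CCS of about 79% to 88%. For 98/196 this is 63% at 79%, 65% at 80%, 75% at 86% and 80% at 88%. Show the halt allowed in Section 3.1 as well: with 77/196, 74% at 88% and 69% at 86%. Make clear that the requirement of at least 80% is met only at about 88% with the full 98/196.

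The cost is a rewrite of one section, and stated power that is less favourable. The restatement itself needs no extra patients. The sizes in the table for 80% power at lower rates show the scale of the gap and are not a request to enlarge the trial.
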